In this first pilot study, the aim is to investigate in healthy adults whether increased exercise changes the haemoglobin values, the collagen content remains constant and repeated measurements at different positions and by different examiners over time provide consistent measurement results. This information is essential for planning further studies in children with neuromuscular disorders, and to be able to evaluate a possible response to therapy.

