## Graphical presentation of study design

## 9. Study population

### **Inclusion and exclusion criteria**

#### ***Inclusion criteria:***

Healthy volunteers:

- Adult (>18 years of age) participants

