### **Participant number**

As this is a pilot study, it is not possible to calculate the exact number of cases. It is planned to examine a total of 10 healthy volunteers.

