### Measurements

[figure not shown]
After informing of the subjects, all study participants are imaged by MSOT at 3 positions of 2 anatomical muscle regions on both sides (right and left): upper/lower leg, on predefined muscle groups (leg proximal: Musculus quadriceps, distal: Musculus gastrocnemius). The examination is performed by two independent examiners directly one after the other. The examination is performed analogous to sonography over the corresponding skin layers without further invasive procedures. The anatomical region can be localized by means of built-in B-scan sonography; the corresponding optoacoustic signals can be recorded in parallel. Each examiner performs two repetitive scans per muscle position. The duration per anatomical region is limited to 5 minutes; this corresponds to a maximum of 20 minutes for both lower extremities. The subjects can remain in a relaxed body position during the examination; assistance in the form of breathing manoeuvres or similar is not necessary. Subsequently, a 6-minute walk test is performed to test muscle activation. Afterwards another examination with MSOT is carried out analogous to the above mentioned procedure. The same procedure is repeated after 14 days.

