## 12. Biometrics

### **Explorative study: explanation of the statistical methodology, justification of the selected number of cases**

#### ***Case number calculation:***

As this is a pilot study and no information on the expected differences between the different groups is available yet, no case number calculation was performed. The number of cases given represents an estimate.

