Non-invasive molecular imaging to determine the hemoglobin and collagen content in muscles before and after physical exercise and over time (MSOT_muscles)

Unique Protocol ID: 169_19B

ClinicalTrials.gov Identifier: NCT03979157

Version date: 23.04.2019

Sponsor:

Department of Pediatrics and Adolescent Medicine
University Hospital Erlangen
Friedrich-Alexander-University (FAU) Erlangen-Nürnberg
Pediatric Experimental and Translational Imaging Laboratory (PETI-Lab)
[name]
[name]
[contact]

Statistical Analysis Plan

The present study is a pilot proof-of-concept study. Due to lack of clinical trials in this area, the comparative changes of MSOT spectra and signals within and between examiners, before and after exercise, over time and between different muscles and muscle positions are unknown. Therefore, no sample size calculation was performed.

The primary outcome measure is to assess the reproducibility of the muscular optoacoustic spectra of healthy volunteers facing different variables (examiner, time, exercise, muscle position).

MSOT signals are derived from averaged video captures (seven frames) obtained in anatomical independent muscle regions in patients. All anatomical locations are considered independent. In cases of multiple scans/recordings, a mean of all analyzed scans is calculated.

Continuous variables are given as means and standard deviations; categorical variables are provided as numbers and percentages. Data are tested for normal distribution using Shapiro-Wilk test prior to inferential analysis. MSOT signals are compared matched manner using a paired t-test when parametric and a Wilcoxon matched-pair signed rank test when non-parametric. For the comparison of three or more groups analysis of variance (ANOVA) and for nonparametric distribution Friedman Test is used. Correlations are specified with the parametric Pearson correlation coefficient (r) and the nonparametric Spearman correlation (r_s), using a 95% confidence interval. Additionally, the intraclass correlation coefficient (ICC) will be used with the grading proposed by Landis and Koch. For all analysis an error level of $p < 0.05$ is considered as statistically significant. All analyses are performed using GraphPad Prism (Version 8, GraphPad Software, La Jolla, CA, USA) and/or IBM SPSS Statistics (Version 24, IBM Corp., N.Y., USA).

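### Reproducibility is the SAP's primary outcome, but its only agreement index is a graded ICC, which depends on the spread of the sample; no measurement error in signal units is planned

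*SAP*

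**What the plan says.** The SAP names reproducibility in healthy volunteers, across examiner, time, exercise and muscle position, as its primary outcome measure. The methods it lists are means with SDs, paired t or Wilcoxon tests, ANOVA or Friedman tests, and Pearson or Spearman correlations. It then adds: "Additionally, the intraclass correlation coefficient (ICC) will be used with the grading proposed by Landis and Koch". It does not give the ICC model, whether the unit is a single scan or a mean of scans, or the cut-points of the grading. The protocol's statistical methods (section 12) mention no agreement measure.

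Two other SAP rules bear on the ICC. All anatomical locations are treated as independent, and "In cases of multiple scans/recordings, a mean of all analyzed scans is calculated".

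On the sample, the protocol's inclusion criterion is "Adult (>18 years of age) participants" and its exclusion criteria rule out signs of myopathy. Under Participant number: "It is planned to examine a total of 10 healthy volunteers". Under Measurements (section 10), two examiners scan three positions of two muscles on both sides, before and after the 6-minute walk test, and the whole procedure is repeated after 14 days. For the repeats: "Each examiner performs two repetitive scans per muscle position".

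On purpose, section 5 of the protocol ends: "This information is essential for planning further studies in children with neuromuscular disorders, and to be able to evaluate a possible response to therapy". The benefits paragraph in section 11 puts it more cautiously, saying that the differences could be important for planning further studies.

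**The concern.** To plan a later study, or to judge whether a patient's signal has really changed, one needs the size of the measurement noise in the units of the signal. An ICC does not give that. It is the between-unit variance divided by the total variance, so the same noise earns a high or a low grade depending on how different the sampled units happen to be.

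The other planned methods do not fill the gap. With 10 volunteers, a paired test that finds no significant difference does not show agreement. A high correlation can coexist with a constant offset between examiners. The planned means and SDs describe spread across observations, not error within a person.

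As written, the study could therefore report its primary outcome as a verbal grade and never state the measurement error, although the design collects the repeats needed to estimate it.

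**Working it through.** **Inputs from the documents.** 10 volunteers (protocol, Participant number); 2 scans per position by each of 2 examiners, repeated after 14 days (protocol, Measurements). Neither document gives a within-subject SD, a between-subject SD, an expected ICC or a precision target. On the sample size, the protocol says "no case number calculation was performed. The number of cases given represents an estimate". So there is no planned figure to reproduce.

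**Assumptions.** The within-subject (error) SD, SDw, is set to 1 unit. The between-subject SD, SDb, is ranged from 0.5 to 3.

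**Step 1: ICC and repeatability coefficient side by side.**

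ICC = SDb² / (SDb² + SDw²). Repeatability coefficient (RC) = 1.96 × √2 × SDw.

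| SDb | ICC | RC |
|---|---|---|
| 0.5 | 0.25 / 1.25 = 0.20 | 1.96 × 1.414 × 1 = 2.77 |
| 1 | 1 / 2 = 0.50 | 2.77 |
| 2 | 4 / 5 = 0.80 | 2.77 |
| 3 | 9 / 10 = 0.90 | 2.77 |

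The RC is constant because SDw was held constant. The table shows only that the ICC moves when the error does not.

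Simulation of 20,000 studies per row, with 10 subjects and 2 repeats, agrees: median ICC 0.19, 0.50, 0.80 and 0.90, and median RC between 2.67 and 2.69 in every row.

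**Step 2: the unit of analysis.** There are 3 positions × 2 muscles × 2 sides = 12 locations per person. If the ICC is run over locations treated as independent, SDb becomes the spread among locations. It then includes differences between muscles, sides and positions. The ICC can move along the table in Step 1 for that reason alone, even if the volunteers are alike.

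**Step 3: the averaging rule.** The ICC of the mean of two scans is 2 × ICC / (1 + ICC). A single-scan ICC of 0.50 becomes 1.00 / 1.50 = 0.67, and 0.60 becomes 1.20 / 1.60 = 0.75. The unspecified unit therefore also moves the grade. Once the two scans are averaged, the difference between them, which is the intra-examiner error, can no longer be estimated.

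**Step 4: precision at n = 10 with 2 repeats (one-way ICC, exact F limits).** F = (1 + ICC) / (1 − ICC). Divide F by 3.78 (97.5% point of F on 9 and 10 df) for the lower value, multiply it by 3.96 (on 10 and 9 df) for the upper value, and convert each back with (F − 1) / (F + 1).

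- Observed ICC 0.80: F = 9; values 2.38 and 35.7; 95% interval 0.41 to 0.95.
- Observed ICC 0.60: F = 4; values 1.06 and 15.9; 95% interval 0.03 to 0.88.

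For the within-subject SD on 10 df, the limits are √(10 / 20.48) = 0.70 and √(10 / 3.25) = 1.75 times the estimate.

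**The case against.** The best defence is that this is a declared exploratory pilot, that every hypothesis and objective in section 6 concerns healthy volunteers, and that the ICC is one addition to a longer list of methods. No threshold, decision or conclusion about patients hangs on the grade. On this view an absolute error measure would be useful, but its absence is not a fault.

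Much of that stands, and it rules out several stronger readings that a reader might reach.

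- **That the study sets out to say what change is real in children with Duchenne muscular dystrophy (DMD), and fails to.** That is the downstream purpose, not a stated question.
- **That enrolling healthy adults is itself an error.** It is an open design choice for a first study.
- **That the collagen ICC will come out low because healthy adults are alike.** The protocol describes connective tissue and fat replacing muscle in DMD, but gives no variance for either group. If locations are pooled, the ICC could equally be high.
- **That the healthy-adult error SD carries over to patients.** Nothing in the documents supports equal error in such different tissue. If the error grows with the signal, an absolute figure and a percentage figure cannot both carry over unchanged.

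What the defence does not answer is narrower. Reproducibility is the SAP's primary outcome, the ICC is the only listed method that measures agreement, and no error in signal units is planned to accompany it.

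**Conclusion.** The point holds as a gap between the chosen statistic and the SAP's own primary outcome. The grade depends on the spread of the units sampled and on two unstated choices: volunteers or locations as the unit, and single or averaged scans. In the illustration, an unchanged error yields an ICC anywhere from 0.20 to 0.90. That range rests on assumed SDs; the dependence on spread is algebra and does not.

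The grade is also weakly determined. With 10 subjects and 2 repeats, an observed ICC of 0.80 is compatible with values from 0.41 to 0.95. The grading cut-points are not in the documents, so this conclusion is about numerical ICCs and not about named grades.

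Nothing here shows that MSOT is poorly reproducible or that the ICC should be removed. The change is worthwhile because it is cheap and the design already collects the data for it.

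**What to change.** In the SAP:

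1. For each signal (hemo/myoglobin, oxygenation, collagen, lipid), report the within-subject SD and the repeatability coefficient, 1.96 × √2 × within-subject SD, in arbitrary units and as a percentage of the mean.
2. Do this separately for repeat scan by the same examiner, for different examiners, and for the 2-week interval. Give 95% intervals that take the volunteer, not the location, as the unit.
3. Exempt the repeat scans from the averaging rule for the intra-examiner analysis.
4. Keep the ICC as a descriptive result with its 95% interval. State its model, and whether it refers to single or averaged scans and to volunteers or locations.
5. State that the ICC and the error estimates both apply to healthy adults, and that error in children with DMD needs its own estimate.

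**Cost.** SAP wording, one exception to an existing rule, and a small analysis of data the protocol already collects. The headline becomes a number in signal units, which is less familiar than a verbal grade. It will also be imprecise: with 10 volunteers and 2 repeats, the 95% interval for the within-subject SD runs from about 0.70 to 1.75 times the estimate.

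### The SAP grades the ICC for its primary reproducibility outcome without an explicit confidence interval, without linking grade to uncertainty, and with all anatomical locations treated as independent

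*SAP*

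**What the plan says.** The SAP defines its main question as follows: "The primary outcome measure is to assess the reproducibility of the muscular optoacoustic spectra of healthy volunteers facing different variables", the variables being examiner, time, exercise and muscle position. The analysis paragraph lists paired tests, ANOVA or Friedman tests, and Pearson and Spearman correlations "using a 95% confidence interval". The next sentence reads "Additionally, the intraclass correlation coefficient (ICC) will be used with the grading proposed by Landis and Koch". The SAP does not give the grade limits, the form of the ICC, an interval for it, or whether the grade is read from the estimate or from a confidence limit. It also states that anatomical locations count as independent.

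On numbers, protocol section 9 (Participant number) says "It is planned to examine a total of 10 healthy volunteers". Section 12 adds "The number of cases given represents an estimate", and the SAP confirms "Therefore, no sample size calculation was performed". Protocol section 10 (Measurements) describes three positions on two muscles on both sides, two scans per position by each examiner, and a repeat after 14 days. On the examiners it says "The examination is performed by two independent examiners directly one after the other".

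**The concern.** A verbal grade turns a continuous estimate into a category by fixed cut points. If the sampling error of the ICC is wider than a category, the word conveys more certainty than the data hold. The ICC is the only agreement coefficient that the SAP names for its primary outcome: a high Pearson correlation or a non-significant paired test does not show agreement. Protocol sections 3 and 5 say that these results are needed for studies in children with neuromuscular disorders. A grade that circulates without its interval could make a signal of middling reproducibility look established.

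The independence statement adds a second risk. If locations are pooled as separate units, any interval computed in the usual way will look narrow, although only 10 people supply the data.

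**Working it through.** **Inputs.** n = 10 volunteers (protocol section 9). k = 2 readings for examiner, repeat scan and visit, and k = 3 for muscle positions (section 10). Locations: 3 positions × 2 muscles × 2 sides = 12 per volunteer, 120 in total. *Assumptions:* cut points 0.2, 0.4, 0.6 and 0.8; single-measure consistency ICC; normal data; true ICC unknown, so several values are shown. The plan has no precision calculation to reproduce.

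**Interval, volunteer as unit.** For an observed ICC r:
- F = [1 + (k − 1)r] / (1 − r)
- Divide F by the 97.5% point of F with (n − 1, (n − 1)(k − 1)) df for the lower bound. Multiply it by the 97.5% point with the df reversed for the upper bound.
- Convert each back by (F − 1) / (F + k − 1).

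k = 2, r = 0.80: F = 1.8/0.2 = 9, and the 97.5% point with 9 and 9 df is 4.026.
- Lower: 9/4.026 = 2.235, giving 1.235/3.235 = 0.38.
- Upper: 9 × 4.026 = 36.23, giving 35.23/37.23 = 0.95.

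This interval reaches four of the five assumed grades.

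k = 3, r = 0.80: F = 2.6/0.2 = 13, with 97.5% points 2.929 (9, 18 df) and 3.701 (18, 9 df). The interval is 0.53 to 0.94, three grades.

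k = 2, r = 0.90: F = 19, interval 0.65 to 0.97, two grades.

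**Chance that a point-estimate grade is wrong, n = 10.** For k = 2, P(estimate < c) = P(F with 9, 9 df < [(1 + c)/(1 − c)] / [(1 + ρ)/(1 − ρ)]), where ρ is the true ICC. At ρ = 0.7 the divisor is 1.7/0.3 = 5.667.
- c = 0.6: 4/5.667 = 0.706, probability 0.306.
- c = 0.8: 9/5.667 = 1.588, probability 0.749.
- Correct grade: 0.749 − 0.306 = 0.443, so wrong in 56%.

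| True ICC | Wrong, k = 2 | Too favourable, k = 2 | Wrong, k = 3 |
|---|---|---|---|
| 0.50 | 70% | 34% | 61% |
| 0.70 | 56% | 25% | 47% |
| 0.85 | 32% | 0 | 32% |
| 0.90 | 14% | 0 | 12% |
| 0.95 | 2% | 0 | 1% |

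**Pooling 120 locations as independent (k = 2, ICC 0.70).** F = 5.667, and the 97.5% point with 119 and 119 df is 1.435. The nominal interval is 0.60 to 0.78. If locations are truly independent, the same formula gives a wrong grade in 3.5%, about 4%. I simulated the case where part of the true between-location variance is shared within a volunteer (8,000 runs per row; independent runs differ by about one percentage point):

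| Share of true variance between volunteers | Wrong grade | Coverage of naive 95% interval |
|---|---|---|
| 0 | 4% | 95% |
| Half | 14% | 84% |
| All | 38% | 59% |

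**The case against.** Four points deserve weight. First, the SAP does not say that the grade is read from the point estimate. The interval wording comes just before the ICC sentence and could be meant to carry over. That stands: grading on the estimate is an inference. Even on the generous reading, though, no rule connects interval and grade.

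Second, the SAP does not fix 10 as the n for the ICC, and its independence statement points to more units. That also stands, and it lowers the wrong-grade risk at a true 0.70 from 56% to between 4% and 38%. It does not remove the problem, because the same statement makes the naive interval too narrow whenever volunteers differ.

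Third, this is an exploratory pilot. No decision depends on the grade, the ICC enters as an addition to other analyses, and the protocol's primary objective is a comparison before and after exercise and over time. This limits the consequence. It does not justify a category shown without its uncertainty.

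Fourth, a reader might infer that the grade should be set by the lower confidence limit. With n = 10 and k = 2, that holds over-favourable grades to at most 2.5%. But correct grades fall from 44% to 6% at a true 0.70 and from 86% to 17% at 0.90. It exchanges two-sided error for near-systematic under-grading, and nothing in the documents calls for it.

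**Conclusion.** The point holds as a gap in the SAP: a graded ICC for the primary outcome has no explicit interval, no link between grade and uncertainty, and no unit of analysis that respects the volunteer. With volunteers as the unit, an observed 0.80 is compatible with roughly 0.38 to 0.95 (0.53 to 0.94 across three positions). With pooled locations, nominal 95% coverage at a true 0.70 can fall to between 84% and 59%.

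A reader might go further and conclude that the reported grade will often be wrong and too favourable. The documents do not support that without conditions. The true ICC is unknown. At about 0.90 or more the grade is wrong in 14% of studies or fewer, and above 0.80 it cannot be too favourable because the top grade is already the true one. Protocol section 5 cites good precision and reproducibility on a slightly different prototype, so high values cannot be ruled out.

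The figures rest on the assumed cut points, normal data and a single-measure consistency ICC. A one-way ICC moves the limits by at most about 0.04.

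**What to change.** Add to the SAP: each ICC is reported with a 95% confidence interval that takes the volunteer as the unit, using one value per volunteer, or a cluster bootstrap or mixed model by volunteer when locations are pooled; any verbal grade is shown together with the range of grades that the interval covers. State the cut points there as well. Grading on the lower limit need not be required.

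No extra volunteers or scans are needed. The cost is a little more analysis work and less definite grades: with 10 volunteers and two readings, an observed 0.80 would be reported as spanning four of the five assumed grades.
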